5.3. Lifestyle Considerations

5.3.1. Meals and Dietary Restrictions

1. Subjects agree to refrain from starting a new diet during the study as described in Section 5.1.
2. Subjects will fast for at least 6 hours prior to dosing on Day 1 and for at least 1 hour following dosing as described in Section 6. During this time, water is permitted.

5.3.2. Caffeine, Alcohol, and Tobacco

1. Subjects will abstain from ingesting any alcohol-containing foods or beverages from 48 hours before Check-in (Day -1) until after the Follow-up Phone Call on Day 21 as described in Section 5.2.
2. Subjects are permitted to ingest caffeine- or xanthine-containing products (eg, coffee, tea, cola drinks, and chocolate), but should limit intake to ≤ 3 cups per day.
3. Subjects who use tobacco products will be instructed that use of nicotine-containing products (including nicotine patches) will not be permitted while they are in the CRU.

5.3.3. Activity

1. Subjects agree to refrain from making any new or major lifestyle changes (eg, exercise regimen) as described in Section 5.1.
2. Subjects must follow contraception requirements outlined in Section 5.1.
3. Prior to dosing, subjects will be encouraged to empty their bowels, if possible.
4. After dosing, subjects will lie on their left side for at least 30 minutes (including for vital signs collection), followed by at least 30 additional minutes in the semisupine position as outlined in Section 6.1.1. Subjects should avoid using the bathroom and hold in the enema for at least 1 hour.
5. For vital sign collection during the Clinic Period, positional and activity restrictions at each timepoint are noted in the SoA (Table 1) and Section 8.2.2.

5.4. Screen Failures

Screen failures are defined as subjects who consent to participate in the clinical study but are not subsequently randomized. A minimal set of screen failure information is required to ensure transparent reporting of screen failure subjects to meet the Consolidated Standards of Reporting Trials (CONSORT) publishing requirements and to respond to queries from regulatory authorities. Minimal information includes demography, screen failure details, eligibility criteria, and any SAE.

Individuals who do not meet the criteria for participation in this study (screen failure) may be rescreened following consultation with the sponsor. Rescreened subjects should be assigned a separate subject number for each screening; once a subject number has been assigned it must not be reused.

6. STUDY INTERVENTION

Study intervention (also referred to as “study drug”) is defined as any investigational intervention(s), and may include marketed product(s) or placebo, intended to be administered to a study subject according to the study protocol.

The study will evaluate multiple-ascending doses of IW-3300 in a double-blind manner. The 9 subjects within each cohort will be randomized to receive multiple doses of IW-3300 (6 subjects) or placebo (3 subjects), administered rectally (as a low-volume [20 mL] enema) following a fast of at least 6 hours. The planned cohorts are:

- Cohort 1: IW-3300 100 µg or matching placebo rectal dose once daily
- Cohort 2: IW-3300 300 µg or matching placebo rectal dose once daily
- Cohort 3 (optional): IW-3300 >100 µg but <300 µg or matching placebo rectal dose once daily (decision to enroll this cohort will be determined after safety reviews of previous cohorts, in the case of intolerance at 300 µg but tolerability at 100 µg)

Dosing in Cohort 2 and optional Cohort 3 will only proceed following a review of safety data from the previous cohort(s), including AEs, clinical laboratory test results, vital signs, and 12-lead ECGs. The determination of dose escalation will be made at a meeting of the Dose Escalation Committee.

Treatment duration will be 7 days; subjects will be followed in the Phase 1 CRU for the duration of dosing, until at least 24 hours after the last dose of study drug and contacted by phone for follow-up approximately 2 weeks after the last dose. Total subject participation will be 29 to 57 days, including the Screening, Clinic, and Follow-up Periods.

6.1. Study Interventions Administered

Intervention Name	IW-3300	Placebo
Type	Drug	Placebo
Dose Formulation	Solution	Solution
Unit Dose Strengths (Solution Concentrations)	[REDACTED]	N/A
Dosage Levels	100 µg, 300 µg, and (optional) <300 µg dose TBD	N/A
Route of Administration	Rectal enema	Rectal enema
Use	Experimental	Placebo
IMP and NIMP	IMP	IMP
Sourcing	Compounded in the pharmacy at the clinical site	Compounded in the pharmacy at the clinical site
Packaging and Labeling	Study Intervention will be provided in filled syringes. Each syringe will be labeled as required per country requirement.	Study Intervention will be provided in filled syringes. Each syringe will be labeled as required per country requirement.

IMP=investigational medical product; NIMP=noninvestigational medical product; TBD=to be determined

6.1.1. Dosing Instructions

Subjects will receive a single dose of study drug (IW-3300 or placebo low-volume enema) in the CRU on Day 1 through Day 7. Study drug will be administered rectally after a fast of at least 6 hours (water is permitted). Subjects will be encouraged to empty their bowels in the morning prior to dosing, if possible. Subjects will be instructed to lie on their left side with their left leg extended and their right leg slightly bent. Study drug will be dispensed in capped syringes with a separately packaged colon tip applicator. The CRU dosing staff will remove the cap from the syringe, attach the colon tip applicator, prime the syringe and applicator to 20 mL, and slowly administer by inserting the contents of the syringe into the rectum. After the full dose has been administered, subjects will lie on their left side for at least 30 minutes to allow the liquid to distribute throughout their intestines, followed by at least 30 additional minutes in the semisupine position. CRU staff will monitor subjects for leakage of the study drug from the rectum during the initial 30 minutes postadministration. Subjects should avoid using the bathroom and hold in the enema for as long as possible (at least 1 hour).

CRU staff will record the date and time of study drug administration in the electronic case report form (eCRF). CRU staff will also record (as yes/no) if there was study drug leakage from the rectum in the 30 minutes following drug administration.

6.2. Preparation/Handling/Storage/Accountability

All study drug substance will be stored in the locked, limited access, temperature-controlled pharmacy accessible only to pharmacy staff. IW-3300 drug substance will be protected from

moisture and light and stored between -25°C to -15°C. Prior to compounding, IW-3300 drug substance will be thawed for a minimum of 30 minutes prior to use.

The investigational drug product may be compounded on the day of administration and stored at room temperature prior to dosing (continuous mixing not required). If the investigational drug product is stored for more than 24 hours, it must be stored refrigerated (2°C to 8°C) for no longer than the product shelf life. Refrigerated drug product must be equilibrated to room temperature for at least 30 minutes prior to dosing. Compounding and storage of the drug product must occur in accordance with the instructions provided in the [Pharmacy Manual](#). Specifically designated unblinded CRU pharmacy staff will be responsible for preparing dosing for each cohort and providing doses to the study coordinator to administer to subjects (see Section [6.1.1](#) for dosing instructions).

Storage and accountability of study drug should adhere to the following:

1. The investigator or designee must confirm appropriate temperature conditions have been maintained during transit for all study drug received and any discrepancies are reported and resolved before use of the study drug.
2. Only subjects enrolled in the study may receive study drug and only authorized site staff may supply or administer study drug. All study drug must be stored in accordance with the labeled storage conditions.
3. The investigator, institution, or the head of the medical institution (where applicable) is responsible for study drug accountability, reconciliation, and record maintenance (ie, receipt, reconciliation, and final disposition records).
4. Further guidance and information for the final disposition of unused study drug are provided in the [Pharmacy Manual](#).

6.3. Measures to Minimize Bias: Randomization and Blinding

6.3.1. Randomization

The subject identification (SID) number will be assigned in an ascending sequential order (eg, beginning with 001, 002, etc.) at the time the subject signs the ICF. The subject will retain the same unique SID number throughout the Clinic and Follow-up Periods.

Subjects who meet all of the inclusion criteria and none of the exclusion criteria will be randomized into the study on Day 1. A total of up to 27 subjects (up to 3 cohorts of 9 subjects each) will be randomized in a 2:1 ratio to receive IW-3300 (N=6) or placebo (N=3), for each cohort, as detailed in Section [6.1](#). Randomization numbers encoding the subjects' treatment assignments will be based on a randomization schedule that is computer-generated prior to the study, by an independent statistician from the CRO who is not otherwise associated with the study. The randomized treatment allocation for each subject will be contained in a sealed, opaque envelope opened at the time of the subject's randomization.

6.3.2. Blinding

The investigator and all other CRU staff, sponsor study personnel, and the subject will remain blinded to individual subject treatment assignments throughout the study, except as noted below.

The Dose Escalation Committee, which will include sponsor and CRO representatives, will conduct blinded reviews of all the safety/tolerability parameters of the dosing cohort through Discharge (Day 8) in order to make decisions regarding subsequent dosing.

Specific designated personnel in the Ironwood Global Patient Safety Group may be unblinded to the treatment assignment of individual subjects for regulatory reporting purposes. All other sponsor study personnel, except as described, will remain blinded until the study is complete and the database is locked, unless warranted by emerging safety or tolerability issues.

Specifically designated unblinded CRU pharmacy staff will be responsible for preparing dosing for each cohort and providing doses to the study coordinator to administer to subjects. The investigator (except as detailed in the next paragraph) and the remaining CRU staff will be blinded as to treatment. In the event of a Quality Assurance audit, the auditor(s) will be allowed access to unblinded study intervention records at the CRU to verify that randomization/dispensing has been done accurately.

Site unblinding of a subject's treatment assignment is restricted to emergency situations that necessitate identifying the study drug for the welfare of the subject. Subject safety must always be the first consideration in making such a determination. If the investigator decides that unblinding is warranted, the investigator, or person designated by the investigator, should contact the sponsor's medical monitor directly to discuss the need for emergency unblinding. Individual sealed unblinding envelopes, which can be opened to identify the treatment assignment for an individual subject in an emergency, will be provided to and retained by the CRU pharmacist. The reason for breaking the blind will be recorded.

6.4. Study Intervention Compliance

Subjects will receive study drug directly from the investigator or designee, under medical supervision. The date and time of each dose administered in the clinic will be recorded in the source documents and recorded in the eCRF. The dose of study drug and study subject identification will be confirmed at the time of dosing by a member of the CRU staff other than the person administering the study intervention.

6.5. Concomitant Therapy

Subjects must abstain from taking prescription medications during the 14 days before Check-in (Day -1) until after completion of the Follow-up Phone Call on Day 21; over-the-counter medications (including laxatives, vitamins, and dietary or herbal supplements) during the 7 days before Check-in (Day -1) until after Discharge on Day 8; and licensed vaccines during the 14 days before Check-in (Day -1) until after completion of the Follow-up Phone Call on Day 21.

Acetaminophen at doses of ≤ 3 grams/day is permitted for use during the study at the investigator's discretion, in consultation with the medical monitor.

Any medication (including over-the-counter or prescription medicines, vitamins, and/or herbal supplements) or vaccine that the subject is receiving at the time of Screening or receives during the study must be recorded along with:

- Reason for use
- Dates of administration, including start and end dates

- Dosage information, including dose and frequency

The medical monitor should be contacted if there are any questions regarding concomitant or prior therapy.

6.5.1. Rescue Medicine

Not applicable to this study of healthy subjects

6.6. Dose Modification

The decision to proceed to the 300- μ g dose level of IW-3300 (Cohort 2) will be made by the Dose Escalation Committee, based on blinded safety and tolerability data obtained through Discharge on Day 8 in all subjects at the 100- μ g dose level (Cohort 1). The decision to proceed with an optional 3rd cohort will be made by the Dose Escalation Committee based on blinded safety and tolerability data for both Cohorts 1 and 2. The dose will be IW-3300 >100 μ g but <300 μ g.

Dosing at a given dose level may be temporarily suspended for any of the reasons listed in Section [7.1.1](#).

6.7. Intervention After the End of the Study

There is no study intervention following the end of the study.

Subjects with ongoing AEs or other safety concerns will be followed until resolution or until no further queries or follow-up actions are required; at the discretion of the investigator, subjects with ongoing safety concerns may have discharge delayed if necessary for continued monitoring.

7. DISCONTINUATION OF STUDY INTERVENTION AND SUBJECT DISCONTINUATION/WITHDRAWAL

7.1. Discontinuation of Study Intervention

It may be necessary for a subject to permanently discontinue study drug. A subject will be discontinued from study drug in the event of:

- A confirmed pregnancy
- A SAE considered by the investigator or Sponsor to be related to study drug

Dosing of study drug for an individual subject may be suspended temporarily as detailed in Section 7.1.1; if the subject is unable to resume dosing, they should follow the instructions for permanent discontinuation below.

If study drug is permanently discontinued, then the subject will have the safety evaluations scheduled for Discharge (Day 8) performed. See the SoA ([Table 1](#)) for data to be collected at the time of discontinuation and follow-up, and for any further evaluations that need to be completed.

If a subject is discontinuing study drug due to an AE, the AE must be followed until it is resolved, stable, or judged by the investigator to be not clinically significant.

7.1.1. Study Suspension or Termination

Dosing may be temporarily suspended for either dose level if any of the following occur within a cohort:

- ≥ 1 subject with an SAE considered related to study drug
- ≥ 1 subject with an National Cancer Institute Common Terminology Criteria for Adverse Events (NCI-CTCAE) Grade 3 or higher AE considered related to study drug (CTCAE v5.0 will be used; grading criteria are summarized in Appendix 3/ Section [10.3.3.2](#))
- ≥ 3 subjects with CTCAE Grade 2 or higher AEs considered related to study drug

The Dose Escalation Committee should consider the benefit-risk ratio in their determination to suspend dosing temporarily or permanently. If the benefit-risk ratio is considered unacceptable and the effect related to active study drug by the Dose Escalation Committee, dosing at a given dose level will be stopped, and no additional cohorts will be dosed at the same or higher dose level (a lower dose could still be studied).

The sponsor may permanently terminate the study, or a component of the study, at any time. Reasons for termination may include, but are not limited to:

- Death, SAE, or other safety finding considered to be related to IW-3300 that may preclude further dosing

7.2. Subject Discontinuation/Withdrawal from the Study

- A subject may withdraw from the study at any time at his/her own request or may be withdrawn at any time at the discretion of the investigator for safety, behavioral, compliance, or administrative reasons. This is expected to be uncommon.
- At the time of discontinuation from the study, if possible, an ET visit should be conducted, as shown in the SoA ([Table 1](#)). See the SoA for data to be collected at the time of study discontinuation and follow-up and for any further evaluations that need to be completed.
- The subject will be permanently discontinued both from the study intervention and from the study at that time.
- If the subject withdraws consent for disclosure of future information, the sponsor may retain and continue to use any data collected before such a withdrawal of consent.
- If a subject withdraws from the study, he/she may request destruction of any samples taken and not tested, and the investigator must document this in the site study records.

7.3. Lost to Follow-up

A subject will be considered lost to follow-up if he or she repeatedly fails to return for scheduled visits and is unable to be contacted by the study site.

The following actions must be taken if a subject fails to return to the clinic for a required study visit:

- The site must attempt to contact the subject, reschedule the missed visit as soon as possible, counsel the subject on the importance of maintaining the assigned visit schedule, and ascertain whether or not the subject wishes to and/or should continue in the study.
- Before a subject is deemed lost to follow-up, the investigator or designee must make every effort to regain contact with the subject (where possible, 3 telephone calls and, if necessary, a certified letter to the subject's last known mailing address or local equivalent methods). These contact attempts should be documented in the subject's medical record.
- Should the subject continue to be unreachable, he/she will be considered to have withdrawn from the study and reason for discontinuation will be "lost to follow-up."

Discontinuation of the site or of the study as a whole are handled as part of Appendix 1/ Section [10.1](#).

8. STUDY ASSESSMENTS AND PROCEDURES

- Study procedures and their timing are summarized in the SoA ([Table 1](#)). Protocol waivers or exemptions are not allowed.
- Immediate safety concerns should be discussed with the sponsor immediately upon occurrence or awareness to determine if the subject should continue or discontinue study drug.
- Adherence to the study design requirements, including those specified in the SoA ([Table 1](#)), is essential and required for study conduct.
- All screening evaluations must be completed and reviewed to confirm that potential subjects meet all eligibility criteria. The investigator will maintain a screening log to record details of all subjects screened and to confirm eligibility or record reasons for screening failure, as applicable.

8.1. Efficacy Assessments

Efficacy will not be evaluated in this Phase 1 study in healthy subjects.

8.2. Safety Assessments

Planned timepoints for all safety assessments are provided in the SoA ([Table 1](#)).

8.2.1. Physical Examinations

Physical examinations will be performed as outlined in the SoA ([Table 1](#)), by the investigator or a licensed health professional listed on Form FDA 1572.

- A complete physical examination will include, at a minimum, assessments of the general appearance of the subject and the HEENT (head, eyes, ears, nose, and throat), cardiac, respiratory, gastrointestinal, musculoskeletal, neurological, and dermatological systems.
- Rectal examination at all timepoints should include a digital rectal examination and visual inspection of the perianal area for redness or irritation. If significant redness, rectal pain, fever, bleeding, or mucus is observed, anoscopy may be performed as part of the rectal examination.
- On Days 1 through 7, the physical examination will be symptom-directed and conducted prior to study drug administration.
- Height and weight will also be measured and recorded at the timepoints noted in the SoA ([Table 1](#)).
- Investigators should pay special attention to clinical signs related to previous serious illnesses, which will be reason for exclusion from the study.
- Any physical examination abnormality that the investigator considers to be potentially clinically significant and changed from baseline will be reported as an AE.

8.2.2. Vital Signs

Vital signs will be performed as outlined in the SoA ([Table 1](#)).

- Vital signs will include oral temperature, blood pressure, and pulse rate.
- Blood pressure and pulse measurements will be assessed with a completely automated device. Manual techniques will be used only if an automated device is not available.
- In a semisupine position, blood pressure and pulse will be obtained at the 0.5-hour postdose timepoint on Days 1 and 7 (consistent with the position required following dosing).
- Blood pressure and pulse at the 2-, 4-, and 8-hour postdose timepoints on Days 1 and 7, as well as predose on Days 3 through 6, should be preceded by at least 5 minutes of rest for the subject in a quiet setting without distractions (eg, television, cell phones).
- At all other timepoints (ie, Day 1 predose and 1- and 6-hours postdose, Day 2 predose, Day 7 predose and 1- and 6-hours postdose, and Day 8 [24-hours post-Day 7 dose]), orthostatic blood pressure and pulse measurements will be obtained. Subjects must lie quietly for \geq 5 minutes before supine/semisupine blood pressure and pulse measurements are taken, then assume standing position for 3 minutes before standing blood pressure and pulse measurements are taken. If a subject has orthostatic symptoms upon standing (eg, palpitation, dizziness), they will be assisted and asked to lie down without waiting the 3 minutes for vital sign assessment. Orthostatic measurements may be taken at other vital signs collection timepoints if clinically indicated, at the discretion of the investigator.
- When applicable, vital signs measurements will be obtained before blood draws.

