7.3. Vital Signs

Descriptive statistics for body weight and vital signs (ie, oral temperature, supine systolic and diastolic blood pressure, and pulse) and changes from baseline values at each time point will be presented by treatment group, and all the data will be listed. If there are multiple measurements for the same time point, the first one will be used for the by-time point analysis.

The number and percentage of subjects with PCS postbaseline vital signs will be tabulated by treatment group (or cohort). A vital sign value will be considered PCS if it meets both the observed value criterion and the change from baseline criterion. The criteria for PCS vital sign values are detailed in [Table 3](#). The PCS percentages will be calculated relative to the number of subjects with baseline values and at least 1 assessment in the postbaseline period. The numerator will be the total number of subjects with available baseline values and at least 1 postbaseline PCS value.

A supportive data listing for subjects with PCS postbaseline values will be provided, including the subject ID number, baseline and postbaseline values for each visit, and a flag indicating the PCS vital sign values.

Table 3: Criteria for Potentially Clinically Significant Vital Signs

Vital Sign Parameter	Flag	Criteria ^a	
		Observed Value	Change from Baseline
Supine systolic blood pressure (mmHg)	High	≥180	Increase of ≥20
	Low	≤90	Decrease of ≥20
Supine diastolic blood pressure (mmHg)	High	≥105	Increase of ≥15
	Low	≤50	Decrease of ≥15
Supine pulse (beats per minute)	High	≥120	Increase of ≥15
	Low	≤50	Decrease of ≥15
Weight (kg)	High	-	Increase of ≥7%
	Low	-	Decrease of ≥7%

^a A postbaseline value is considered as a PCS value if it meets the criteria for both observed value and change from baseline.

In addition to supine measurements, at the predose measurement and at various postdose time points on days 1, 2, 7 and 8, standing blood pressure and pulse will be measured 3 minutes after the supine measurements are taken. The change in blood pressure from supine to standing, along with associated adverse events, will be used to assess orthostatic hypotension. The criteria for testing positive for orthostatic hypotension are presented in [Table 4](#).

Table 4: Criteria Associated with Orthostatic Hypotension

Blood Pressure Parameter	Blood Pressure Change from Supine to Standing
Systolic blood pressure (mmHg)	Decrease of ≥20 mmHg
Diastolic blood pressure (mmHg)	Decrease of ≥10 mmHg

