Subjects meeting either one of these two criteria and who also have an associated adverse event, as indicated on the eCRF, are considered to be positive for orthostatic hypotension. The number and percent of subjects who have an orthostatic hypotension event will be tabulated by treatment group (or cohort) and by period (baseline versus postbaseline).

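### A standing test stopped for orthostatic symptoms yields no planned standing blood pressure, so that timepoint cannot count towards the SAP's orthostatic hypotension table, which is biased towards zero where intolerance is greatest

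*Protocol*

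**What the plan says.** Protocol 8.2.2 and footnote f of the Schedule of Activities (repeated in SAP 11.3) describe the orthostatic procedure. Subjects lie quietly, have a supine or semisupine reading, "then assume standing position for 3 minutes before standing blood pressure and pulse measurements are taken". If symptoms such as dizziness or palpitation occur on standing, "they will be assisted and asked to lie down without waiting the 3 minutes for vital sign assessment". No earlier or substitute standing reading is specified.

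SAP 7.3 states that "The change in blood pressure from supine to standing, along with associated adverse events, will be used to assess orthostatic hypotension". Table 4 sets the blood pressure criteria: systolic "Decrease of ≥20 mmHg" or diastolic "Decrease of ≥10 mmHg". The case definition then joins the two parts: "Subjects meeting either one of these two criteria and who also have an associated adverse event, as indicated on the eCRF", are positive. Positive subjects are tabulated by treatment group (or cohort) and by baseline or postbaseline period. The SAP does not say what happens when the standing value is missing, how a stopped test is classified, or what the denominator is.

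**The concern.** For a positive result the SAP needs both a measured fall and an adverse event. The protocol, for good reason, ends the standing test in subjects who develop symptoms. At that timepoint the value is missing because of the condition the table is meant to count, so the missingness is informative and its direction is known.

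Protocol 2.3.1 names orthostatic measurements as a means of evaluating volume depletion, under the class risk of diarrhea and dehydration. A zero in this table could be read as reassurance about a dose when one or more standing tests in that group were in fact stopped for symptoms.

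Dropping the adverse event condition would not help. These subjects lack the blood pressure change, not the adverse event.

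**Working it through.** The plan gives no rate, power or sample size calculation for this table, so there is no figure to reproduce. The check applies the SAP definition to the data that the protocol produces.

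**Step 1. One subject, one timepoint**
- Supine value: obtained.
- Symptoms on standing: the subject lies down and the planned 3-minute value is not taken.
- Change = standing minus supine: cannot be calculated.
- Table 4 (systolic fall of at least 20 mmHg or diastolic fall of at least 10 mmHg): cannot be met.
- Associated adverse event: may be present.
- SAP rule (Table 4 and adverse event): not met, so the subject is not counted at this timepoint.

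An early reading does not clearly rescue the case. The SAP describes only a 3-minute value and times it differently from the protocol: "standing blood pressure and pulse will be measured 3 minutes after the supine measurements are taken", whereas the protocol counts the 3 minutes from standing up. Whether an earlier value would be accepted is not stated.

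**Step 2. Timepoints (Protocol 8.2.2)**
- Baseline: Day 1 predose = 1.
- Postbaseline: Day 1 at 1 and 6 h (2) + Day 2 predose (1) + Day 7 predose, 1 and 6 h (3) + Day 8 (1) = 7.

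One qualifying postbaseline reading is enough for a subject to be counted. A subject is lost only if none of the 7, and no unscheduled measurement, qualifies.

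**Step 3. Effect in one active group (n = 6)**
- One such subject missing from the count: 0/6 = 0% (exact 95% CI 0 to 45.9%).
- The same subject counted: 1/6 = 16.7% (exact 95% CI 0.4% to 64.1%).

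**Step 4. Illustration over assumed rates**

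The documents give no rates. Let p be the per-subject probability of symptomatic orthostatic hypotension. Let s be the share of those cases with no qualifying reading at any postbaseline timepoint. Then P(table shows at least one case) = 1 − (1 − p(1 − s))^6.

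| p | s = 0 | s = 0.5 | s = 1 |
|---|---|---|---|
| 10% | 46.9% | 26.5% | 0% |
| 20% | 73.8% | 46.9% | 0% |
| 30% | 88.2% | 62.3% | 0% |

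For example, p = 20% and s = 0.5 gives 1 − 0.9^6 = 46.9%, against 1 − 0.8^6 = 73.8% when every case is measured.

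**The case against.** The strongest reply has five parts.

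- **An early reading is not forbidden.** The protocol waives the wait and does not prohibit a measurement while the subject is still upright. This stands: the accurate statement is that no standing value is planned, not that none can exist. But none is required, and the SAP does not say whether one would be used.
- **The loss is per timepoint.** A reader might infer that a subject with symptoms can never be counted. The documents do not support that. There are 7 scheduled postbaseline chances, and further orthostatic measurements are allowed at the investigator's discretion. A single episode, or one that stops the test each time, is still lost.
- **The safety signal survives elsewhere.** A reader might infer that the event disappears from the report. It does not. A symptom reported as an adverse event is tabulated by preferred term, grade and relationship (SAP 7.1), and all vital signs are listed (SAP 7.3). Dose escalation rests on blinded review of all safety parameters, and the suspension criteria use related SAEs and graded adverse events (Protocol 6.6 and 7.1.1), not this table. The primary endpoints are unaffected. However, a preferred term such as dizziness would not show that a standing test had been stopped.
- **Symptoms without a blood pressure are not established orthostatic hypotension.** The 1-hour test follows a fast of at least 6 hours and about an hour lying down, so dizziness may have another cause. This also stands. It is why 1/6 above is an upper figure, and why stopped tests should not simply be scored positive: that would drop the blood pressure criterion for these subjects alone.
- **The eCRF is not available here.** It may already record why a reading was not done.

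**Conclusion.** The point holds as a gap between the protocol procedure and the SAP definition. Followed as written, the plan leaves a symptom-stopped standing test unable to qualify at its timepoint, and the resulting bias in the orthostatic hypotension table is towards zero.

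In a group of 6, each subject with no qualifying postbaseline reading can lower the count by up to one, or 16.7 percentage points. That size assumes that no early, later or unscheduled reading qualifies and that the symptom truly reflected orthostatic hypotension. How often tests will be stopped is unknown.

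A reader might go further and conclude that a true 1/6 will be reported as 0/6, or that the clearest cases are removed from the safety evaluation. The documents support neither. The true count cannot be known without a blood pressure, the SAP does not say whether a subject with no reading is scored negative or excluded, and the adverse event outputs remain. The effect is confined to one descriptive safety table in a study with no hypothesis testing. It is still worth correcting, because the table addresses a named risk and the correction is small.

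**What to change.** Leave the lie-down instruction unchanged. In SAP 7.3:

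1. Keep the present definition (Table 4 fall plus associated adverse event) for confirmed orthostatic hypotension.
2. Add a separate row, by treatment group and period: *standing assessment stopped or not obtained because of orthostatic symptoms*.
3. Add a combined count as a sensitivity summary: confirmed orthostatic hypotension or a symptom-stopped test, each subject counted once.
4. Define the denominator as subjects with at least one attempted standing assessment in the period, and state that a symptom-stopped test is not scored as negative.
5. State how a standing reading taken before 3 minutes is handled, and reconcile the SAP's timing of the standing reading with the protocol's.

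If the eCRF does not already do so, record the reason a standing reading was not done and any standing value obtained before 3 minutes.

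The cost is a few sentences in the SAP, two table rows and possibly one reason code and one data field. Design and sample size do not change. The downside is that some vasovagal or unrelated dizziness will appear in the separate row and the combined count; keeping these apart from the confirmed count makes that visible.
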